8.6 INDEPENDENT MEDICAL REVIEWER

Evaluation and adjudication of all AEs will be performed on an ongoing basis by an independent medical reviewer. The independent medical reviewer will review AEs for AE classification, seriousness, and relationship to the device or procedure. Discrepancies between the investigational site and the independent medical reviewer will be handled by discussion, with the determination by independent medical reviewer serving as the final classification.

8.7 DATA SAFETY MONITORING BOARD

A Data Safety Monitoring Board (DSMB) will oversee enrollment and safety of the subjects for the study. Members of DSMB will be independent of the sponsor and investigational sites. The DSMB for the study will consist of three (3) clinicians with expertise in orthopedic or plastic surgery, and with experience and expertise in clinical trials. The DSMB will convene at least once during the subject enrollment period and will review, at a minimum, subject enrollment status and incidence of AEs. Based on a review of these data, the DSMB will advise the Sponsor to continue the trial with no modification, or to modify the trial as appropriate if enrollment or safety concerns are identified.

9. RISK-BENEFIT ANALYSIS

9.1 **RISK ANALYSIS**

Complications and risks that exist for other CTR treatments may also exist for the UltraGuideCTR technique. The UltraGuideCTR technique has undergone extensive risk analysis testing and is designed with safeguards built into the device to mitigate the serious risks. The full list of anticipated adverse events is provided on the Adverse Event CRF. All complications that can occur with mOCTR may also occur with CTR-US.

9.2 **POTENTIAL BENEFITS**

The data obtained from this study will be used to document the safety and effectiveness of UltraGuideCTR and compare it to mOCTR. The data derived from this study may benefit individuals with CTS in the context of a shared-decision making process when contemplating CTR. In addition, subjects potentially could directly benefit from participation in this study. UltraGuideCTR is designed to provide relief from CTS through a less invasive approach than mOCTR. Previous publications reported that patients may experience significant symptom relief and return to activities within 3-5 days post-procedure, which is faster than typically reported for mOCTR.

10. DATA ANALYSIS

This is a multicenter, randomized, controlled trial designed to evaluate the safety and effectiveness of CTR-US compared to mOCTR in treating subjects with symptomatic CTS. Eligible subjects will be randomized (2:1) to receive CTR-US ($n \approx 80$) or mOCTR ($n \approx 40$).

10.1 SAMPLE SIZE JUSTIFICATION

The results of the power analysis provided a sample size consisting of 102 evaluable subjects. Group sample sizes of 68 and 34 achieve 80% power to reject the null hypothesis of zero effect size when the population effect size is 0.60 and alpha is 0.05 using a two-sided two-sample equal-variance t-test with a 2:1 randomization allocation. To account for reasonable subject attrition, 120 subjects (n≈80 CTR-US, n≈40 mOCTR) will be enrolled in the trial.

10.2 ANALYSIS POPULATIONS

The primary statistical analyses will be performed on a modified intention-to-treat population, which will be comprised of all subjects who meet all study eligibility criteria, are subsequently randomized, and receive their assigned treatment. Randomized subjects who withdraw from the study prior to treatment or who receive the incorrect treatment will not be included in the modified intention-to-treat population.

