6.2 SUBJECT SELECTION

Patients with suspected CTS will be consecutively evaluated for study eligibility at each site. Patients must meet all inclusion criteria and no exclusion criteria to be enrolled in the trial.

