6.2.2 Exclusion Criteria

- 1. Prior surgery on the target wrist or hand with the exception of trigger finger that has clinically recovered
- 2. History of prior surgical CTR in the target hand
- 3. History of prior surgical CTR in the contralateral hand within 3 months of enrollment or with persistent symptoms that interfere with normal daily activities or work at the time of consent
- 4. Corticosteroid injection in the target wrist or hand within 6 weeks of study procedure date
- 5. Presence of additional process in the target wrist or hand requiring additional intervention beyond carpal tunnel release (e.g. neurolysis, mass removal, tenosynovectomy)

- 6. Clinically significant degenerative arthritis of the upper limb (shoulder to hand) on the target side
- 7. Clinically significant inflammatory disease (including tenosynovitis) of the upper limb (shoulder to hand) on the target side
- 8. Clinically significant trauma or deformity of the upper limb (shoulder to hand) on the target side
- 9. Clinically significant vascular disease (including Raynaud's phenomenon) of the upper limb (shoulder to hand) on the target side
- 10. Clinically significant neurological disorder (including complex regional pain syndrome) of the upper limb (shoulder to hand) on the target side
- 11. Planned surgical or interventional procedure on the contralateral wrist or hand
- 12. Systemic inflammatory disease (e.g., rheumatoid arthritis, lupus)
- 13. Amyloidosis
- 14. Chronic renal insufficiency requiring dialysis
- 15. Diabetes not controlled by a stable dose of medication over the past three months
- 16. Uncontrolled thyroid disease
- 17. Pregnant or planning pregnancy in the next 12 months
- 18. Workers compensation subjects
- 19. Inability to provide a legally acceptable Informed Consent Form and/or comply with all follow-up requirements
- 20. Subject has other medical, social or psychological conditions that, in the opinion of the investigator, preclude them from receiving the pre-treatment, required treatment, and post-treatment procedures and evaluations

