6.3 RANDOMIZATION

Subjects meeting all study inclusion/exclusion criteria after their screening evaluation will be randomized. This study will enroll 120 subjects who will be randomized in 2:1 fashion to receive CTR-US (n≈80) or mOCTR (n≈40). The randomization sequence for this trial will be computer-generated by the electronic data capture system (Viedoc). The randomization

sequence will be stratified by site with variable block sizes. Treatment assignment will be concealed until it is presented to authorized site personnel at the time of randomization. Only randomized and treated subjects will be considered enrolled in the study. Randomized patients who do not receive their assigned treatment will be discontinued from the trial.

6.4 **BLINDING**

Owing to obvious differences in surgical technique, it is not possible to blind the treating physicians. Owing to notable visual differences in the postoperative scar between surgical techniques (3-5 mm for CTR-US and approximately 3 cm for mOCTR), it is not possible to blind the subjects. Owing to the fact that all data collected in this trial will be self-reported, it is not possible to blind outcome assessors (i.e., subjects).

6.5 **PROCEDURE**

The key procedural steps involved in CTR-US are listed below.

- 1. Using direct US visualization, identify relevant anatomical structures within the carpal tunnel.
- 2. Dissect synovial tissue from the undersurface of the TCL via hydrodissection.
- 3. Insert the device through a small wrist incision and advance into the carpal tunnel.
- 4. Position the tip of the device distal to the distal TCL so that the TCL Blade will engage the distal TCL.
- 5. Confirm the position of the device under ultrasound.
- 6. Activate the Stealth MicroGuard balloons to create space within the carpal tunnel.
- 7. Deploy the TCL Blade by moving the slide button proximally to transect the TCL from distal to proximal until the TCL Blade passes into its proximal recessed position.
- 8. With the device or an elevator, probe the TCL to ensure a complete release.

Complete procedural details are provided in the Instructions for Use (https://sonexhealth.com/physicians/ultraguidectr/instructions-for-use).

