6.7 FOLLOW-UP ASSESSMENTS

A list of the study assessments performed by the investigational site at each study interval is provided in the table below.

Assessment	Baseline Screening	Procedure	Post- Op	Day 7	Day 14	1 month	3 months	6 months	12 months
Demographics	√								
Ultrasound median nerve cross-sectional measurement	٧								
CTS-6 (both hands)	1								
Randomization	√								
Procedure		√							
Image of incision		√							
Adverse events		√	1	1	1	1	√	√	√

A list of the patient reported outcomes provided by the patient at each study interval is provided in the table below.

Assessment	Baseline Screening	Procedure	Post-Op	Daily 1-14	1 month	3 months	6 months	12 months
Demographics	√							
Medical history	√							
BCTQ-SSS	√			√1	1	1	1	1
BCTQ-FSS	√			√1	√	1	1	1
EQ-5D-5L	√			√1	1	1	1	1
Numeric Pain Scale	√	√	√	1	1	1	1	1
Procedure		√						
Images of wound healing				$\sqrt{2}$	1	√	√	√
Return To Activities (RTA)				1	1	√	√	√
Return To Work (RTW)				1	√	√	√	√
Pain Medication	√	√	√	1	√	√	√	-√

¹Collected at 14-day evaluation

²Collected at Day 7 and Day 14

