11.9.3 Protocol Deviations

A protocol deviation is an unplanned excursion from the protocol that is not implemented or intended as a systematic change. If an investigator failed to perform tests or examinations as required by the protocol or there were failures on the part of study subjects to complete scheduled visits as required by the protocol, would be considered protocol deviations. These types of deviations are reported to the sponsor and in accordance with the IRB policy.

A Protocol Deviation CRF must be completed by the site for each study protocol deviation (e.g., failure to obtain informed consent, enrolling a subject who does not meet inclusion / exclusion criteria, not performing required testing, missed follow-up window, etc.). An Investigator must notify the Sponsor and the reviewing IRB of any deviation from the study protocol that was done to protect the life or physical well-being of a subject. Such notice should be given as soon as possible, but no later than five (5) working days after the emergency occurred.

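### Section 10.2 makes meeting all eligibility criteria a condition of the only analysis set without limiting it to what was known before randomisation, so correctly treated subjects found ineligible later can be left out

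*Combined protocol and SAP*

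**What the plan says.** Section 10.2 gives a single population for the primary analyses, a modified intention-to-treat set "comprised of all subjects who meet all study eligibility criteria, are subsequently randomized, and receive their assigned treatment". Its next sentence names two kinds of removal: "Randomized subjects who withdraw from the study prior to treatment or who receive the incorrect treatment will not be included" in the set. The plan defines no all-randomised, per-protocol or safety set.

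Eligibility appears in several other places:

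- Section 6.2: "Patients must meet all inclusion criteria and no exclusion criteria to be enrolled in the trial". Section 6.3 adds that a subject counts as enrolled only once randomised and treated.
- Section 6.3: "Subjects meeting all study inclusion/exclusion criteria after their screening evaluation will be randomized". The first schedule table in Section 6.7 puts randomisation in the baseline screening column.
- Section 6.2.2, exclusion 5: "Presence of additional process in the target wrist or hand requiring additional intervention beyond carpal tunnel release (e.g. neurolysis, mass removal, tenosynovectomy"). No time of assessment is given.
- Section 6.2.2, exclusion 4: "Corticosteroid injection in the target wrist or hand within 6 weeks of study procedure date". This is counted from a date that falls after randomisation.
- Section 6.2.4: the procedure may take place more than 30 days after screening, in which case the questionnaires are repeated. A repeat eligibility check is not mentioned.
- Section 11.9.3 lists "enrolling a subject who does not meet inclusion / exclusion criteria" as an example of a protocol deviation. It does not say whether that subject stays in the analysis.

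Section 6.4 states that neither treating physicians nor subjects can be blinded.

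**The concern.** Membership of the only analysis set depends on an attribute that can be reassessed after randomisation by people who know the arm. The example that fits the text best is exclusion 5. A mass or tenosynovial process first seen during the operation was probably there at screening. The subject therefore did not meet all criteria, even though nobody knew it when the subject was randomised, and the assigned procedure was then performed.

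If such subjects are removed, the removal rests on a finding made after randomisation with treatment known. A process that needs further intervention could plausibly slow recovery, so those removed may not be typical of their arm. The return-to-activity, return-to-work, BCTQ, pain and EQ-5D-5L comparisons would then be made between groups that differ from the groups randomised and treated. Whether this happens, how often, and in which arm cannot be learned from the documents.

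**Working it through.** **Step 1. When the eligibility condition has any effect.** Section 6.3 lets only subjects who pass screening be randomised, and Section 6.2.3 stops screen failures before randomisation. For a subject whose eligibility was judged correctly at screening, the first clause of Section 10.2 adds nothing. It changes the set only when a randomised subject is later found ineligible. For that case the plan does not say when, by whom or on what information eligibility is fixed for the analysis.

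**Step 2. Two readings of Section 10.2 applied to the two criteria.**

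| Situation, assigned procedure received | Eligibility as it stood before randomisation | Eligibility as known at analysis |
|---|---|---|
| Exclusion 5 process already present, first seen at surgery | Left out: the criterion was failed, though unrecognised | Left out |
| Exclusion 4 first failed after randomisation (injection while waiting, or procedure date moved) | Kept | Left out |

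The exclusion 5 case fails on both readings. The exclusion 4 case depends on the reading, so it shows ambiguity and no more.

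**Step 3. The plan's own figure.** Section 10.1 gives 68 and 34 evaluable subjects, effect size 0.60, two-sided alpha 0.05 and a two-sample t-test. The noncentrality is 0.60 × √(68 × 34 / 102) = 2.86 on 100 degrees of freedom, which gives power of 80.8%. The next smaller exact 2:1 pair, 66 and 33, gives 79.6%. Enrolment of 120 equals 102 / 0.85. These figures reproduce and are not in dispute.

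**Step 4. Size, on assumed counts.** The documents give no rate for late-found ineligibility, so everything below illustrates scale and is not an estimate.

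- Weight of one subject: 1/40 = 2.5% of mOCTR; 1/80 = 1.25% of CTR-US.
- Return by day 3, assuming 12 of 40 in mOCTR: 12/40 = 30.0%. Removing one non-returner gives 12/39 = 30.8%; removing three gives 12/37 = 32.4%.
- Related adverse events, assuming 3 of 40 in mOCTR and that one affected subject is removed from the denominator as well: 3/40 = 7.5% becomes 2/39 = 5.1%.
- Removal unrelated to outcome, power at effect size 0.60: from 80/40, losing 2 or 4 mOCTR subjects moves power from 86.7% to 85.5% or 84.2%. From 68/34 it moves from 80.8% to 79.1% or 77.3%.
- Removal related to outcome, moderate case: if a fraction f of an arm is removed and those removed are on average g SD worse than those kept, the arm mean moves by f × g. Two of 40 (f = 0.05) with g = 0.5 gives 0.025 SD; with g = 1.0 it gives 0.05 SD.
- Removal related to outcome, upper bound: always drop the slowest recoverers, with no true effect, normal outcomes, a t-test, 80/40 and 40,000 simulated trials.

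| Dropped | Shift in the contrast | Two-sided type I error |
|---|---|---|
| None | 0 | 5% |
| 2 of 40 mOCTR | 0.10 SD against CTR-US | 9% |
| 4 of 40 mOCTR | 0.19 SD against CTR-US | 17% |
| 2 of 80 CTR-US | 0.06 SD towards CTR-US | 7% |
| 4 of 80 CTR-US | 0.11 SD towards CTR-US | 10% |

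The simulation uses the t-test of Section 10.1, not the Fisher, Mann-Whitney and mixed-model analyses of Section 10.5, so it shows order of magnitude only. Loss unrelated to outcome costs little. Selective loss is what matters.

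**The case against.** The strongest reply is that Section 10.2 does not order these removals. Its clauses run in time order, eligibility first and randomisation after it, and Section 6.3 settles eligibility after screening. The sentence on removals names withdrawal before treatment and incorrect treatment, not late-found ineligibility. Sections 6.8 and 11.9.3 do not call for it either: the first does not list it as a reason for withdrawal, and the second treats it as a deviation to be recorded.

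Much of this stands for exclusion 4. A failure that first arises after randomisation does not, on the natural reading, remove the subject. A contrary reading is open, because Section 6.2 makes eligibility a condition of enrolment and Section 6.3 completes enrolment only at treatment, but it is not the obvious one. The reply does not cover exclusion 5, where the process was probably present before randomisation. The second sentence of Section 10.2 does not say its list is complete, and it re-admits nobody who fails the first.

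Two further objections are right against stronger readings:

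- A reader might infer that the two techniques reveal extra pathology at different rates, since Section 6.4 gives scars of 3-5 mm and about 3 cm. The documents do not support this. Sections 3 and 6.5 describe imaging throughout CTR-US, with a view of the carpal tunnel at least as good, and every target hand is scanned at baseline. No mechanism is given for exclusion 4 to fail more often in one arm.
- A reader might infer that adverse events in subjects found ineligible go uncounted. Sections 8.5 to 8.7 record, adjudicate and review adverse events with no eligibility condition, and Section 10.5 reports them per subject by group without tying them to the modified set. What is missing is only a stated denominator.

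**Conclusion.** The point holds as a weakness in the definition of the analysis set. Read literally, Section 10.2 leaves out a subject who was randomised and correctly treated but is later found ineligible. Exclusion 5 is the clear example. Exclusion 4 adds uncertainty about when eligibility is fixed. Because assignment is open, any such removal would be made with treatment known and could bias the comparison.

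The size is unknown and may be nil. Under the assumed counts, loss unrelated to outcome costs about 1 to 4 points of power. Dropping the 2 or 4 slowest recoverers from one arm shifts the contrast by about 0.06 to 0.19 SD, in either direction depending on the arm; this is an upper bound. The documents do not support saying that removals will be unequal between arms, or that they will favour either procedure. The planned sample size is unaffected.

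The stated removal of subjects who withdraw before treatment or receive the incorrect treatment is a separate departure from intention-to-treat and is not assessed here.

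**What to change.** In Section 10.2, drop the eligibility condition. Define the modified intention-to-treat set as all randomised subjects who receive their assigned procedure, whether or not an eligibility violation is found later. Record such violations as protocol deviations under Section 11.9.3.

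If an analysis without ineligible subjects is wanted, make it a sensitivity analysis. Base it only on information recorded before randomisation, and have eligibility judged without knowledge of arm or outcome. In Section 10.5, state that adverse events are analysed on all treated subjects.

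Exclusions 4 and 5 need no change, because once the condition is removed their timing no longer decides who is analysed. The same edit serves if the sponsor always intended to keep these subjects.

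The cost is a few sentences, with no extra subjects or visits. The downside is that a few ineligible subjects stay in the main analysis and may slightly dilute the contrast.

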4. DEVICE DESCRIPTION

The UltraGuideCTR (Sonex Health, Inc., Eagan, MN) is a commercially available medical device specifically developed to facilitate CTR-US. The device is a single-use, hand-held device that is inserted into the carpal tunnel through a small (typically < 5 mm) wrist incision using continuous US guidance. The working tip of the UltraGuideCTR consists of two inflatable balloons that border a centrally located, retractable retrograde cutting knife. When inflated with sterile saline, the balloons increase the diameter of the tip from 4 mm to 8 mm. After the tip is positioned within the transverse safe zone, the balloons are inflated to create space in the carpal tunnel, the blade is activated, and the TCL is transected in a retrograde manner. Following TCL transection, the blade is recessed, the balloons deflated, and the device is removed. The TCL is probed to ensure a complete release. The entire procedure is performed using US guidance. The first commercial CTR-US procedure with the device was performed in February 2017. Since then, over 100 different physicians have been trained to use the UltraGuideCTR, who collectively have performed over 15,000 procedures. Labeled images of the device are provided below.

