6.2.4 Timing of Patient Screening

All baseline testing and evaluations should be performed as close to the time of the procedure as possible. If the subject's procedure date is more than 30 days from the screening evaluation, subject screening validated questionnaires must be repeated to ensure accuracy of baseline condition at the time of procedure.

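### Subjects who leave between randomisation and surgery drop out of both the only analysis set and the enrolled count, so exclusion can depend on assigned arm and no planned report or analysis would check it

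*Combined protocol and SAP*

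**What the plan says.** **Analysis set.** Section 10.2: "The primary statistical analyses will be performed on a modified intention-to-treat population". Membership requires eligibility, randomisation and receipt of the assigned treatment. The section adds: "Randomized subjects who withdraw from the study prior to treatment or who receive the incorrect treatment will not be included". No other analysis set is defined. Section 10.5 rules out imputation and names no sensitivity analysis.

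**Enrolment and follow-up.** Section 6.3: "Only randomized and treated subjects will be considered enrolled in the study". It continues: "Randomized patients who do not receive their assigned treatment will be discontinued from the trial". Section 10.1 sets the target as 120 enrolled, which under this definition means 120 treated.

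**Timing and knowledge of the arm.** The site schedule in section 6.7 ticks Randomization in the Baseline Screening column, ahead of Procedure. Section 6.3: "Treatment assignment will be concealed until it is presented to authorized site personnel at the time of randomization". Section 6.4 says "it is not possible to blind the subjects". Section 6.2.4 asks for baseline evaluations as near to the procedure as possible, but also provides for the case "If the subject's procedure date is more than 30 days from the screening evaluation", and sets no maximum.

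**Availability of CTR-US.** Section 4 calls the UltraGuideCTR a "commercially available medical device specifically developed to facilitate CTR-US". Section 11.9.5 says the sites purchase it, and section 6.1 requires every investigator to be experienced in both operations.

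**Records.** Section 6.3 has the electronic data capture system generate the randomisation sequence. Section 6.8.1 requires the reason for an official withdrawal to be documented and includes withdrawn subjects' data up to that point. Section 6.9 calls for an End of Study form for each subject.

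**The concern.** The point is confined to subjects who leave before any study procedure, although the rule also removes those given the wrong one. Excluding never-treated subjects does no harm if leaving cannot depend on the assigned arm, for example because the arm is still unknown. Here the assignment exists before surgery, nobody is blinded, and one of the two procedures can be had commercially, possibly from the same surgeon. Section 9.2 describes CTR-US as less invasive, with faster return to activities than is typical for mOCTR. A subject assigned mOCTR therefore has a plausible reason and a route to leave.

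If that happens, the treated mOCTR group is a selected part of those randomised to it, and the comparison loses some of the protection of randomisation. The outcome most exposed is the first main outcome, return to normal daily activities within 3 days, compared by Fisher's exact test. Because leavers are neither enrolled nor analysed, the planned results would not show how many there were or from which arm.

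**Working it through.** **1. The plan's own figure.** Section 10.1: 68 and 34 evaluable, effect size 0.60, two-sided 5%, equal-variance t-test. Noncentrality = 0.60 / √(1/68 + 1/34) = 0.60 / 0.210 = 2.86 on 100 degrees of freedom, which gives 80.8% power. 66/33 gives 79.6%, so 34 is the smallest control arm that reaches 80% at 2:1. 102 / 0.85 = 120. The stated design reproduces. The issue is bias, not power, because the target already counts treated subjects.

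**2. Replacement.** If a share w of mOCTR assignees leaves before surgery, about 40/(1 − w) must be randomised to that arm to treat 40:
- w = 10%: 40/0.9 = 44.4, so 45
- w = 20%: 40/0.8 = 50

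The extra 5 or 10 appear in neither the enrolled count nor the analysis.

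**3. Inputs for the bias illustration.** From the plan: 80 against 40, and Fisher's test at two-sided 5%. Assumed, because the documents give no leaving rate, no mOCTR return rate and nothing on leavers' prognosis: true 3-day return of 40% in both arms, leaving only from mOCTR, and leavers who would have returned at rate r.

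Rate among those who stay = (0.40 − w·r) / (1 − w). For example, w = 0.20 and r = 0.60 gives (0.40 − 0.12)/0.80 = 35%.

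Exact enumeration of Fisher's test over all outcomes at 80/40, with no true treatment effect:

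| w | r | mOCTR stayers | Total error | Favouring CTR-US | Favouring mOCTR |
|---|---|---|---|---|---|
| 0 | – | 40.0% | 4.0% | 2.0% | 2.0% |
| 5% | 60% | 38.9% | 4.2% | 2.7% | 1.5% |
| 10% | 60% | 37.8% | 4.6% | 3.6% | 1.1% |
| 20% | 60% | 35.0% | 7.1% | 6.7% | 0.5% |
| 20% | 70% | 32.5% | 11.2% | 11.0% | 0.2% |
| 20% | 20% | 45.0% | 6.6% | 0.5% | 6.1% |

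**4. Sensitivity to the assumptions.** With a true rate of 50% in both arms (the CTR-US registry median in section 5 is 3 days), total error is 3.4% with no leaving. It is 3.9-5.3% if 10% leave at r = 70-90%, and 5.8-14.0% if 20% leave at the same rates. If 10% or 20% leave from both arms alike at r = 60% (true rate 40%), total error is 4.1%.

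**The case against.** A modified intention-to-treat set without never-treated subjects is common, and section 10.2 declares it openly. That stands, and the set can remain primary.

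Three stronger readings are tempting, and the documents do not support them.

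- **That leavers vanish unseen.** Assignments come from the data capture system, and official withdrawals must be documented with a reason. Leavers should be traceable, although the definition of enrolled leaves it unclear whether the End of Study form reaches them. What is missing is a commitment to report or analyse them.
- **That the comparison tilts toward CTR-US.** Wanting a fast recovery is not the same as recovering fast. If leavers would have returned slowly, the error runs the other way, as the last row of the table shows.
- **That surgery may follow more than 30 days after the arm is known.** The 30 days in section 6.2.4 run from the screening evaluation, and section 6.3 gives no interval between randomisation and surgery. Nor do the documents say when subjects are told their arm. Section 6.3 mentions only site personnel, and section 6.4 rests the lack of blinding on the scar. Disclosure before surgery is the natural reading, but it is an inference.

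The size can also be overread. In the 10% example, the one-directional error rises from 2.0% to 3.6% while total two-sided error stays below the nominal 5%.

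**Conclusion.** The concern holds as a gap in the plan. The stated rules permit exclusion after randomisation that can depend on the arm, and nothing planned would detect it or bound its effect. Bias is possible rather than demonstrated, and its direction depends on who leaves.

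With a true 3-day return of 40% in both arms and leaving only from mOCTR, the effect is small at 10% leaving (total error 4.6% against 4.0%). It becomes material near 20% leaving with selected leavers (7.1-11.2%). With 20% slow-returning leavers, the chance of a false result favouring mOCTR is 6.1%. All leaving rates and return rates here are assumptions. The power calculation is unaffected.

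**What to change.** 1. **Sections 6.3 and 10.2:** account for every randomised subject by assigned arm. Report those who leave before treatment by arm, with reasons and baseline CTS-6, BCTQ and pain scores.
2. **Sections 10.2 and 10.5:** keep the modified intention-to-treat analysis as primary. Add an all-randomised sensitivity analysis of 3-day return that gives leavers opposite extremes by arm: CTR-US leavers not returned with mOCTR leavers returned, then the reverse. State whether the main result survives. Giving both arms the same value would not bound a difference between them. Section 10.3 counts days from treatment, so a leaver has no observed day 3; say that these values are assigned by convention, and exempt this analysis from the no-imputation rule.
3. **Sections 6.3 and 6.7:** state that randomisation takes place after the procedure date is booked and as close to the procedure as site scheduling allows.
4. **Sections 6.8.1 and 10.2:** reconcile the inclusion of withdrawn subjects' data up to withdrawal with the exclusion of those who withdraw before treatment.

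**Cost:** wording, one table, one analysis and a small scheduling burden. No new outcome data are needed. The bounds widen with leaving: 5 leavers among 45 mOCTR assignees move that arm's rate over a range of 5/45 = 11 percentage points, and 10 among 50 over 10/50 = 20 points. With many leavers the bounds could fail to confirm a true result.

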6.8 SUBJECT WITHDRAWAL FROM STUDY

6.8.1 Voluntary Withdrawal

A subject may voluntarily withdraw from the study at any time. If a subject officially withdraws from the study, the investigator must ensure that the reason for the withdrawal is documented. If the subject had an AE, the subject should be followed until the resolution of the AE, if possible. Data from these subjects will be included in the analysis up to the point of each subject's withdrawal.

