6.9 END OF STUDY

Subjects may exit the study at the end of the study (i.e., the study is discontinued by the Sponsor) or when the subject has completed the 12-month follow-up visit, whichever comes first, unless the subject opted to find an alternative treatment.

An End of Study CRF will be completed at the time the study is completed, discontinued, or lost to follow-up for each subject.

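### Randomised subjects who undergo the other study procedure are dropped from the only defined analysis set and discontinued, so they cannot later be analysed as randomised

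*Combined protocol and SAP*

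**What the plan says.** Section 10.2 names a single population, a modified intention-to-treat set "comprised of all subjects who meet all study eligibility criteria, are subsequently randomized, and receive their assigned treatment". It then spells out the exclusion: randomised "subjects who withdraw from the study prior to treatment or who receive the incorrect treatment will not be included". No full intention-to-treat, as-treated, per-protocol or safety set is defined elsewhere, and section 10.5 plans no sensitivity analysis in a different set and no imputation.

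Section 6.3 adds a rule on conduct: "Randomized patients who do not receive their assigned treatment will be discontinued from the trial". Section 6.4 says of the trial that "it is not possible to blind the subjects"; the surgeons are not blinded either, and all outcomes are described there as self-reported. The main recovery outcomes come from electronic questionnaires answered after the operation (sections 6.7, 7.1.1 and 7.1.2).

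**The concern.** Leaving a treated subject out of one analysis set can be repaired later, provided the outcome data exist. Ending that subject's participation cannot be repaired: a day-3 answer that was never asked for cannot be recovered. Sections 10.2 and 6.3 do both to subjects who undergo the other study procedure.

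Such subjects need not resemble the rest of their arm. Surgeon and subject both know the assignment, and a change of procedure may be connected with anatomy, difficulty or preference. Removing these subjects turns the comparison of arms as randomised into one of subjects who received what they were assigned, and the protection of randomisation no longer fully applies.

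The same rule affects safety. Adverse events in a subject who underwent the other procedure fall outside every analysis set that the plan defines.

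**Working it through.** **The plan's own figure.** Section 10.1 gives 68 and 34 evaluable subjects for 80% power at effect size 0.60, two-sided alpha 0.05. Noncentral-t power at 68/34 is 80.8% (79.6% at 66/33), and 102/0.85 = 120. The sample size reproduces and is not in dispute. It contains no crossover rate.

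**Inputs for the illustration.** From the documents: n = 80 and 40 (section 10.1); Fisher's exact test, two-sided 5%, on return to normal activities within 3 days (section 10.5); registry median of 3 days after CTR-US (section 5), used as p = 0.50. Assumed, because the documents give nothing: no true difference (0.50 in both arms); a fraction f of CTR-US subjects excluded for having the other procedure; a proportion q of those excluded back by day 3.

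**Shift.** The proportion among analysed CTR-US subjects becomes (p − f·q)/(1 − f).

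- f = 5%, q = 0: 0.50/0.95 = 0.5263, a shift of 2.6 points.
- f = 5%, q = 25%: (0.50 − 0.0125)/0.95 = 0.5132, a shift of 1.3 points.

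The standard error of the difference is √(0.25/80 + 0.25/40) = 0.0968, or 9.7 points.

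**Rejection rate** (exact enumeration, 80/40 analysed; 3.4% with no exclusions):

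| f | Shift, q = 25% to 0 | Fisher rejection |
|---|---|---|
| 2.5% | 0.6 to 1.3 points | 3.4 to 3.6% |
| 5% | 1.3 to 2.6 points | 3.6 to 4.1% |
| 10% | 2.8 to 5.6 points | 4.2 to 6.7% |

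If the excluded 5% are not replaced (76/40), rejection is 3.8-4.4% against 3.7% without bias. If excluded subjects resemble the rest (q = 50%), the shift is 0. Excluding slow returners from mOCTR instead would move the difference the other way.

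**Price of analysing as randomised.** Assume true 3-day return of 50% on CTR-US against 23% on mOCTR, with 5% of CTR-US subjects crossing over and returning at the mOCTR rate.

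- As randomised, 80/40: the CTR-US proportion is 0.95 × 0.50 + 0.05 × 0.23 = 0.4865; the difference falls from 27.0 to 25.65 points; Fisher power is 77.2%.
- Present plan, 76/40, 50% against 23%: power is 80.7%.

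**The case against.** Three points on the other side carry weight.

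**The effect is small on the figures above.** At 5% excluded, rejection stays under the nominal 5% even if none of those excluded were back by day 3. It passes 5% only at 10% excluded with q = 0. Crossover may also be rare: the treatment is a single operation, section 6.1 requires at least 10 prior cases of each procedure, and assignment is concealed until randomisation. This stands. A reader might infer that the plan inflates type I error, or that the exclusion favours CTR-US. The documents support neither reading, because they give no rate and nothing on how excluded subjects would differ.

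**The text is less absolute than it looks.** Section 10.2 governs the primary analyses and does not forbid another set. Section 6.3 does not say when discontinuation takes effect, and sections 6.8.1 and 6.8.2 keep data up to withdrawal. That is fair, but no other set is defined, and keeping data up to an exit does not supply questionnaires due after it.

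**Modified intention-to-treat sets are common.** A reader might extend the concern to everyone who leaves between randomisation and the operation. That goes too far. Untreated subjects have no day 0 (section 10.3), so the recovery outcomes are undefined for them. Nor is their exit unrecorded: on voluntary withdrawal "the investigator must ensure that the reason for the withdrawal is documented", and "An End of Study CRF will be completed at the time the study is completed, discontinued, or lost to follow-up for each subject". Section 11.9.3 adds that "A Protocol Deviation CRF must be completed by the site for each study protocol deviation". For them the gap is one of reporting.

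An as-randomised analysis also has a fault if used for everything: complications of one procedure would be counted against the other arm. The remedy must therefore treat safety separately.

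**Conclusion.** The concern holds. As written, the plan departs from the randomised comparison for subjects who undergo the other procedure, and it stops the data collection that would allow a later as-randomised analysis.

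The conclusion rests on the wording of sections 6.3 and 10.2 and not on a demonstrated bias. The size and direction of any bias are unknown. The 1.3-2.6 point shift depends on assumed values: 5% excluded from CTR-US only, 0-25% of them back by day 3, 50% return in both arms. It is zero if excluded subjects resemble the rest. This should be fixed because correction is cheap and the missing outcomes cannot be recovered afterwards; it is not a fatal defect.

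The eligibility condition in section 10.2 is a separate matter, and nothing here argues for removing it.

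**What to change.** 1. **Section 6.3:** keep subjects who undergo the other study procedure in study follow-up, so that their questionnaires and adverse events are collected.
2. **Section 10.2, effectiveness:** analyse all eligible randomised subjects who undergo either study procedure, in the randomised arm, converted cases included. Leave the eligibility condition unchanged. Keep the present assigned-treatment set as a sensitivity analysis.
3. **Section 10.2, safety:** define an as-treated set for device- and procedure-related adverse events, so that complications are attributed to the procedure performed.

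**Cost:** protocol and SAP wording, plus the existing electronic questionnaires for a few more subjects. Crossovers dilute the estimate slightly; in the scenario above, power is 77% as randomised against 81% under the present plan. The change to 6.3 helps only subjects not yet discontinued.

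Three minor clarifications could go into the same amendment, although they are not part of the main point: tabulate pre-treatment losses by arm with reasons; define incorrect treatment; and state whether a subject given the other procedure counts toward the 120, since section 6.3 also says "Only randomized and treated subjects will be considered enrolled in the study".
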